### **External validity**

**- Impossibility of replicating the treatments:** the intervention is described in detail and aims to address a problem in clinical practice.

**- Effects of the experimenter:** the research assistant in charge of collecting the data will be masked.

**- Reactive effects of the treatments:** as mentioned in the intervention protocol, this will be developed initially in the context of the health institution and will continue in the normal context of the participant with prior agreement.

- **Interference from multiple treatments:** within the exclusion criteria those who are participating in another research with an educational component different from the usual care are considered.

### **Measurement instruments**

The information collection process will be carried out from the design of a form for the collection of sociodemographic data and clinical conditions of the participants and the application of the instruments for measuring both primary and secondary results:

- Self-management instrument in early stages CKD SM chronic kidney disease: 30 items, 4 factors (self-integration, problem solving, seeking social support and adherence to the recommended regimen), Cronbach's alpha of 0.95; English, Vietnamese, Taiwanese, and Mandarin languages. Likert scale evaluation, possible score from 29 to 116 (28).
- Therapeutic adherence scale EAT: 21 items, 3 factors (control over the intake of drugs and food, medical-behavioral monitoring, and self-efficacy); Cronbach's alpha of 0.92, evaluation on a scale from 0 to 100; Spanish language (29).
- General Self-efficacy Scale: 10 items, Cronbach's alpha of 0.87, in English and Spanish languages (30).

### **APPROACH TO THE ANALYSIS FRAMEWORK**

To respond to specific objectives 1 and 2, a statistical analysis will be carried out through descriptive statistics. Subsequently, a normality test will be carried out, to identify how the data distribution is presented, in addition, it is carried out to determine the tests to be used, whether parametric or non-parametric in the inferential analysis, bivariate and multivariate analysis. A bivariate analysis, to compare the sociodemographic and clinical characteristics between the groups.

To respond to specific objective 3, Inferential statistics will be carried out, which will be carried out to accept or reject the null or alternative hypothesis, which are proposed as:

- H1: The CKD SMS intervention in self-management in people with CKD in early stages is effective on self-management behaviors, self-efficacy, and therapeutic adherence. (H1: G1 > G2; p < 0.05)
- H0: The CKD SMS intervention in people with CKD in early stages is not effective on self-management behaviors, self-efficacy, and therapeutic adherence. (H0: G1 = G2; p > 0.05)

But it is also used multivariate analysis, to determine the individual relationship but also the relationship of the possible variables that intervene on the results, a simple logistic regression model will be built and adjusted according to the possible confounding variables.

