### **Specific objectives**

1. Describe the sociodemographic and clinical characteristics of the control group and the experimental group.
2. Establish the level of self-efficacy, self-management behaviors and therapeutic adherence as a baseline in people with chronic kidney disease in early stages.
3. To evaluate the changes in self-management behaviors, self-efficacy, and therapeutic adherence post-intervention and in the control group at 16 weeks.

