## **METHODOLOGY**

This is a quantitative investigation, with a pragmatic randomized clinical trial (pRCT) design, parallel experimental type, given the one-to-one allocation in two parallel groups with repeated pre-test and post-test measures, considering that this type of study is useful for evaluating interventions in usual care (23). In CKD, the use of a pRCT enables a broader range of patients to be included to test an intervention applicable to patient care and to measure relevant patient-centered outcomes, thus improving external validity and translation of the results into the clinical care (24).

Where the outcome variables are: Self-management behaviors (primary), self-efficacy and therapeutic adherence (secondary). The population will be adult men and women with chronic kidney disease in stages 1-4, who attend control of their disease or belong to the BBraun Avitum Prevenser program.

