### **SAMPLE**

**Sample design:** The sample size was calculated through probability sampling, since individuals have the same probability of being chosen. On the other hand, of the comparison of means in independent groups, assuming a power of 80%, a confidence level of 95%, an expected mean difference of 18.13 in the improvement of self-management, reported by previous studies (6,27).

**Sample size:** A total of 82 participants (41 per group), in addition, a mortality of 20% of the participants is expected, so a total sample of 100 participants (50 per group) will be assumed. made in the Epidat 3.1 program.

**Randomization:** Participants will be randomized into two groups, using sequentially numbered opaque sealed envelopes, where the investigator and participants will be blinded to the allocation of each group. For the generation of the randomization sequence, it will be developed by the investigator by means of the realization of a table of random numbers in the Epidat 3.1 program to eliminate the selection bias, in the same way, said table will be verified to guarantee balance between the number of participants assigned to each group (control and intervention).

**Blinding:** In view of the need to minimize bias, both the participants and the recruitment research assistant will be blinded until allocation. The Result Research Assistant will not have access to the allocation base, nor to the allocation codes. On the other hand, it is

declared that the intervention will be given by the researcher and that the main researcher will also participate in statistical analysis, therefore, the study is classified as single blind.

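### A normality test is left to choose the effect measure, and the plan does not say how the collected baseline score enters the comparison between arms

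*Combined protocol and SAP*

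**What the plan says.** **Choice of test.** In the combined protocol and SAP, the section Approach to the Analysis Framework plans a preliminary check: "a normality test will be carried out, to identify how the data distribution is presented". Its stated purpose is that "it is carried out to determine the tests to be used, whether parametric or non-parametric in the inferential analysis, bivariate and multivariate analysis". The section does not name the normality test, its threshold, the variable tested (pre, post, change or residual) or the comparison used in either branch. The hypotheses set G1 above G2 at p < 0.05 and attach no mean, median or change to those symbols.

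**Sizing.** The Sample section bases the number on "of the comparison of means in independent groups, assuming a power of 80" per cent, with an expected mean difference of 18.13 in improvement of self-management. It gives no SD.

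**Baseline.** The Methodology section describes "two parallel groups with repeated pre-test and post-test measures". Specific objective 3 is "To evaluate the changes in self-management behaviors, self-efficacy, and therapeutic adherence post-intervention and in the control group at 16 weeks". No section says whether the pre-test score is a covariate, is subtracted to form a change, or is left out.

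**Adjusted model.** The only one named is a simple logistic regression adjusted for possible confounders, with no cut-point for the scores. The confounders under Study Variables are age, gender, education, time of diagnosis and comorbidities. The baseline outcome score is not among them.

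**The concern.** The trial is sized to detect a difference in means. If a normality test rejects, the usual two-group alternative is a rank test, and that does not estimate the mean difference used for sizing. What is estimated is then settled only once the data are seen, and self-management, self-efficacy and adherence could end up on different scales. The Blinding paragraph adds weight: the main researcher, who is not blinded, takes part in the statistical analysis, so choices left open now would be made by someone who knows the allocation.

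The second part is precision. Every participant gives a pre-test score. Depending on how it is used, the same number of participants can give clearly different power, and the plan does not commit to any use.

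**Working it through.** **Inputs from the documents.** Mean difference 18.13; power 80%; confidence 95%; 41 per arm, raised to 50 for 20% loss (Sample); scale range 29 to 116 (Measurement instruments). Expected completers: 50 × (1 − 0.20) = 40 per arm.

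**Assumptions, not in the documents.** Two-sided 5% test; SD; pre-post correlation ρ; equal SD before and after.

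**1. The plan's own figure.** The 41 per arm cannot be reproduced forwards without an SD. Solving n = 2(1.960 + 0.842)² SD² / 18.13² for n = 41 gives SD = 18.13 / (2.802 × √(2/41)) = 29.3, an effect of 18.13/29.3 = 0.62 SD. A noncentral-t calculation gives SD 28.9. This is large for the scale: scores spread uniformly over its width of 87 would have SD 87/√12 = 25.1.

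**2. Power by use of baseline.** Power ≈ Φ(18.13 / (s√(2/40)) − 1.960), taking 29.3 as the post-score SD:
- post-only: s = 29.3
- change score: s = 29.3√(2(1 − ρ))
- ANCOVA: s = 29.3√(1 − ρ²)

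| ρ | Post-only | Change: s, power | ANCOVA: s, power |
|---|---|---|---|
| 0.3 | 79.0% | 34.67, 64.8% | 27.95, 82.7% |
| 0.5 | 79.0% | 29.30, 79.0% | 25.37, 89.2% |
| 0.7 | 79.0% | 22.70, 94.7% | 20.92, 97.2% |

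Worked line, ρ = 0.5, ANCOVA: 18.13 / (25.37 × 0.2236) = 3.195; Φ(3.195 − 1.960) = 0.892.

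**3. Smaller SD, ρ = 0.5.**
- SD 25: post-only 18.13/(25 × 0.2236) = 3.243, power 90.0% (89% by noncentral t). ANCOVA s = 21.65, ratio 3.745, power 96.3% (96% by noncentral t).
- SD 20: post-only ratio 4.054, power 98.2% (98.0% by noncentral t). ANCOVA s = 17.32, ratio 4.681, power 99.7% (99.6% by noncentral t).

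**4. What the gate itself does.** Simulation: 4,000 trials per setting, 40 per arm, underlying ρ = 0.5, shift 0.62 SD. A Shapiro-Wilk test in each arm at 5% chose between a t-test and Mann-Whitney on the post score.

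| Score shape | Sent to rank test | Ungated t-test | Gated test | ANCOVA |
|---|---|---|---|---|
| Normal | 9.0% | 78.5% | 78.3% | 88.4% |
| Left-skewed | 91.8% | 77.6% | 81.1% | 87.4% |
| Right-skewed | 98.7% | 78.2% | 88.8% | 87.2% |

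With no true effect, the gated rule rejected in 4.6% to 5.4% of trials and ANCOVA in 4.6% to 5.2%. A second simulation, testing normality on pooled scores at an effect of 0.626 SD, gave 78.2% (gated) against 88.1% (ANCOVA) for normal scores and 92.2% against 87.1% for a skewed shape.

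The shape of the data therefore does decide which quantity is reported. With normal scores, the gated and ungated tests differ by 0.2 points; the roughly 10-point gain appears only when baseline is added.

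**The case against.** Four counter-arguments deserve weight.

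- **Baseline may be intended.** Objective 3 speaks of changes and the sample-size text of improvement, so a change-score comparison fits the documents as well as a post-only one. A reader might infer that the trial discards its pre-test data; the documents do not support that. They leave the use of baseline unstated. If a change score is meant, the gap to ANCOVA at ρ = 0.7 is only 94.7% against 97.2%. If 29.3 is instead the SD of the change, the change test has 79% power, and ANCOVA has 93%, 89% and 85% at ρ = 0.3, 0.5 and 0.7. The advantage then falls as the correlation rises.
- **The gate has some use.** A reader might infer that it is harmful in itself or pointless. Error rates stay near 5%, and with right-skewed scores the rank branch was as powerful as ANCOVA or slightly more so.
- **Non-parametric does not rule out baseline.** A rank test can be run on change scores, and rank-based covariance methods exist. The plan names no specific test, so it cannot be said that this branch is unable to adjust.
- **The SD is back-solved.** With SD 20, a post-only test already has about 98% power, leaving little to gain.

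All four stand as limits on size. None supplies a stated effect measure or a stated role for baseline. The planned logistic regression does not fill the gap either: no dichotomy is defined, and the listed confounders omit the baseline score.

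**Conclusion.** The point holds as a fault of specification with a cost in precision; it is not a failure of validity. The effect measure is data-dependent, does not necessarily match the mean difference used for sizing, and may differ across the three outcomes. How baseline enters the comparison is not stated.

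A reader might infer that the normality test costs the trial about 10 points of power. It does not: the difference between about 79% and 89% at ρ = 0.5 is the gain from baseline adjustment. Over ρ from 0.3 to 0.7 that gain is about 4 to 18 points over a post-only test (82.7 − 79.0; 97.2 − 79.0). It rests on 40 completers per arm, normal scores and a post-score SD of about 29. At ρ = 0.5 it falls to about 6 to 7 points with SD 25 and under 2 with SD 20. Neither the SD nor the correlation is in the documents. The change should be made, but the trial remains interpretable without it if the choice is fixed before the data are examined.

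**What to change.** In the analysis framework:

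1. Remove the normality test as a rule for choosing tests.
2. Pre-specify one primary analysis: a linear model of the week-16 CKD-SM score on arm and baseline CKD-SM score, reporting the adjusted mean difference with 95% CI and robust standard errors.
3. Use the same model for self-efficacy and therapeutic adherence, each with its own baseline score.
4. Keep a rank-based analysis as a sensitivity analysis only, reported whatever the score distribution.
5. State that this linear model, not the simple logistic regression, gives the primary answer. Add any adjustment for the listed confounders to it as a secondary analysis.

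The cost is analysis-plan wording only: no new data, visits or participants, because the baseline scores are already collected. If scores prove strongly skewed, the linear model may give up some power against a rank test (87.1% against 92.2% in the less favourable simulation).

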### **Research question**

How effective is the CKD SMS self-management nursing intervention on self-management behaviors, self-efficacy, and adherence in adults with early-stage CKD compared to usual care?

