### **Hypothesis:**

- Establish that the CKD SMS intervention has a positive effect on self-efficacy and therapeutic adherence in people with early-stage CKD compared to usual care.
- Establish the effectiveness of the CKD SMS intervention in improving self-management behaviors compared to the usual intervention in people with CKD in early stages.

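### The only stated decision rule puts three outcomes into one H1/H0 pair and writes p > 0.05 into the 'not effective' hypothesis, without carrying through that self-management is the primary outcome

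*Combined protocol and SAP*

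**What the plan says.** In the combined protocol and SAP, the section Approach to the analysis framework is the only place that states a decision rule. Inferential statistics are planned, "which will be carried out to accept or reject the null or alternative hypothesis". The alternative says that the intervention "is effective on self-management behaviors, self-efficacy, and therapeutic adherence. (H1: G1 > G2; p < 0.05". The null says that it "is not effective on self-management behaviors, self-efficacy, and therapeutic adherence. (H0: G1 = G2; p > 0.05". The section does not separate primary from secondary outcomes, gives no testing order, names no confidence interval, and does not say what is concluded if the outcomes differ. The choice of test is left open: a normality check is used "to determine the tests to be used, whether parametric or non-parametric".

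Other sections do set a hierarchy. Methodology lists the outcomes as "Self-management behaviors (primary), self-efficacy and therapeutic adherence (secondary". The Hypothesis section gives self-management its own statement: "Establish the effectiveness of the CKD SMS intervention in improving self-management behaviors compared to the usual intervention". The Sample section sizes the trial on that outcome alone, "assuming a power of 80%, a confidence level of 95%, an expected mean difference of 18.13 in the improvement of self-management". Relevance of effectiveness measurement ties effectiveness to self-management, and Measurement instruments again distinguishes primary from secondary results. The Research question, however, asks about the effect "on self-management behaviors, self-efficacy, and adherence in adults with early-stage CKD compared to usual care", that is, about all three together, and the General objective does the same.

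**The concern.** There are two faults, and the first is the clearer.

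First, a hypothesis is a statement about the population, while a p-value describes the sample. Writing p > 0.05 into the null, attaching it to the words 'not effective' and allowing the null to be accepted treats lack of evidence as evidence of no effect. Effectiveness is what the research question asks about, so this label would be the trial's main conclusion.

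Second, one pair for three outcomes works only when all three agree. If self-management is non-significant and adherence is significant, or the reverse, the rule does not say which result carries the label. The answer can be inferred from Methodology, but a pre-stated rule should not need inference.

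**Working it through.** The point concerns wording and structure, so most of the check is a comparison of passages. The plan's 82 evaluable participants (41 per group) are not reproduced here: the Sample section gives no standard deviation, and the point does not depend on that figure.

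**Step 1: does the rule follow the hierarchy?**

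| Section | Role of self-management | Role of the other two outcomes |
|---|---|---|
| Methodology | primary | secondary |
| Hypothesis | own statement on effectiveness | separate statement |
| Sample | basis of the sizing | not used |
| Relevance of effectiveness measurement | what effectiveness refers to | not named |
| Approach to the analysis framework | one of three in a single pair | same standing as the primary |

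The hierarchy is present everywhere it matters except in the decision rule.

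**Step 2: which results does the pair cover?** Each outcome is either significant in favour of the intervention or not, which gives 2 × 2 × 2 = 8 patterns.

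- All three significant: H1 fits (1 pattern).
- None significant: H0 fits (1 pattern).
- Mixed: 8 − 2 = 6 patterns fit neither line as written. Self-management is significant in 4 − 1 = 3 of them and non-significant in the other 3.

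If H0 is read instead as the plain negation of H1, all six mixed patterns become 'not effective', including the three in which the primary outcome is significant. That contradicts Methodology. These are counts of patterns, not probabilities.

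**Step 3: what does p > 0.05 establish?** With a two-sided test at 0.05, p > 0.05 means that the 95% confidence interval, estimate ± half-width, contains zero. Its upper limit is then always above zero, so some benefit is never excluded. Whether the planned difference of 18.13 is excluded depends on precision. A non-significant estimate is smaller than the half-width, so its upper limit is smaller than 2 × half-width. The interval can therefore reach 18.13 only if the half-width exceeds 18.13 / 2 = 9.065. Without a standard deviation the documents do not show on which side of 9.065 the trial will fall. The rule does not look at the interval in either case.

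**Step 4: does correcting the rule change the design?** Testing self-management alone at 0.05 is what the Sample section already assumes (80% power, 95% confidence). If the sidedness of the test matches the sizing, sample size and planned power do not change. Sidedness does need stating: H1 is directional, H0 is an equality, and the Sample section is silent on it.

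**The case against.** The strongest reply is that this is loose phrasing and not a flawed plan. A null hypothesis normally says that there is no effect, and the bracketed p-values may be shorthand for the significance level. The pair may also be shorthand for three separate pairs, with self-management deciding because Methodology says so. The section contains no instruction on how an inconclusive result is to be written up. Study variables plans crude and adjusted estimates and refers to the size of the difference, so the analysis is not confined to p-values. Bias control commits to reporting the expected results.

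Much of this stands. Read naturally, self-management decides. What remains is that the only decision rule, taken at its word, allows a non-effectiveness hypothesis to be accepted on p > 0.05, and that it must be read against other sections to learn which outcome governs. Even the three-pairs reading leaves the first fault in place.

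Three stronger readings are tempting, and the documents do not support them.

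- A reader might infer an inflated false-positive rate, 1 − 0.95³ = 14.3% for three independent tests. That needs a rule under which any one significant outcome counts as success. No such rule is written, and a single primary outcome is named.
- A reader might infer that 1 − 0.80 = 20% of trials with a true difference of 18.13 would be mislabelled. That is simply the planned type II error. It holds only if the unstated standard deviation is the one that gives 80% power at 41 per group, and rewording the hypotheses would not change how often the test is non-significant.
- A reader might infer that the plan commits to publishing a non-significant result as proof of no effect. The text sets a decision rule and gives no reporting instruction.

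**Conclusion.** The point holds as a fault in the stated decision rule. It merges the primary outcome with two secondary ones and equates non-significance with ineffectiveness. Its severity is low to moderate: the fault bears on how the conclusion is labelled, not on data collection, the primary type I error or the sample size.

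No probability of a wrong label can be given from the documents, because that depends on the standard deviation and on how the three outcomes are correlated, and neither is stated. The conclusion assumes only that the analysis section would be applied as written. If the investigators in practice let self-management decide and report intervals, the consequence largely disappears, but the plan should say so.

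**What to change.** Replace the two hypothesis lines before post-test data are seen. Suggested content:

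- The primary conclusion rests on self-management alone. The null is a between-group difference of zero, tested at alpha 0.05, with the sidedness stated and matched to that used for the sizing.
- Self-efficacy and adherence are secondary and are reported separately, so that the rest of the research question is still answered. The sponsor chooses one approach in advance: label them supportive, or test them in a pre-stated order only after a significant primary test.
- p-values are removed from the hypotheses themselves.
- Between-group estimates with 95% confidence intervals are reported for all three outcomes, with the estimator named if a non-parametric test is used.
- A result with p > 0.05 is described as no effect demonstrated, not as showing that the intervention does not work.

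The cost is a rewording and one check of the sidedness used in the sizing. No new data are needed, and with sidedness matched the sample size is unchanged. The downside is that no confirmatory claim can be made on a secondary outcome if the primary test fails.

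### The only adjusted model named is a logistic regression, but all three outcomes are scores and no event, cut-off or ordinal form is defined

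*Combined protocol and SAP*

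**What the plan says.** - **Adjusted model.** Under Approach to the Analysis Framework, after the hypotheses for objective 3, "a simple logistic regression model will be built and adjusted according to the possible confounding variables". The dependent variable is not stated, and a model called simple sits oddly with one that is adjusted.
- **Other inferential analysis.** The same section uses a normality test to "determine the tests to be used, whether parametric or non-parametric in the inferential analysis, bivariate and multivariate analysis", and writes the alternative for all three outcomes as "H1: G1 > G2; p < 0.05".
- **Objective.** Specific objective 3 is to "evaluate the changes in self-management behaviors, self-efficacy, and therapeutic adherence post-intervention and in the control group at 16 weeks".
- **Outcomes.** Under Measurement instruments the self-management scale has "Likert scale evaluation, possible score from 29 to 116". Adherence is scored from 0 to 100. Self-efficacy is a 10-item scale with no range given. No cut-off or ordered category appears for any of them.
- **Sample size.** The Sample section relies on "the comparison of means in independent groups, assuming a power of 80" per cent, with "an expected mean difference of 18.13 in the improvement of self-management". No SD is given.
- **Who analyses.** The Blinding paragraph says that "the main researcher will also participate in statistical analysis". The Bias Control section adds that delivery of the intervention and analysis will probably both fall to the main investigator, who cannot be blinded.
- **Confounders.** Study Variables lists age, gender, education, time of diagnosis and comorbidities, and plans to compare crude with adjusted estimates. It names no model.

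**The concern.** A logistic model needs a binary or an ordered outcome. The plan supplies scores and no rule for turning them into either, so two analysts following it to the letter could produce different adjusted results from the same data.

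Three things are at stake:

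1. The adjusted result would depend on a cut that may be picked after the data are seen, by someone who knows the allocation.
2. An odds ratio cannot be set beside the 18.13-point mean difference on which the trial was sized. The crude-versus-adjusted comparison in Study Variables would then mix two scales.
3. Splitting a score at a cut discards information and costs power.

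**Working it through.** **1. The text.** The trial is sized on means, the objective concerns changes, the instruments give scores, and the adjusted model is logistic. The normality test does not bridge the gap: it chooses between parametric and non-parametric tests and supplies neither a dependent variable nor a cut. An ordinal logistic model would need no cut, but none is named.

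**2. The plan's own figure.** For two means, n per group = 2(z₁₋α/₂ + z₁₋β)² SD²/δ². With δ = 18.13, 80% power and 5% two-sided, the stated 41 per group cannot be reproduced, because no SD is given. Solved backwards:

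SD = 18.13 / [(1.960 + 0.842) × √(2/41)] = 18.13 / 0.619 ≈ 29.3.

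The t-based version gives about 28.9. A one-sided test gives about 33. After 20% losses, 50 × 0.80 = 40 per group.

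**3. Is SD 29 plausible?** The score runs from 29 to 116, a width of 87. A uniform spread over the whole range has SD 87/√12 = 25.1, so SD 29 would need scores piled up at both ends. Centre the two arms on the scale midpoint of 72.5, at 72.5 ± 9.065. For a normal score in the lower arm (mean 63.4) with SD 29, the part outside the range is Φ(−34.4/29) + Φ(−52.6/29) ≈ 0.118 + 0.035, about 15%. The other arm is symmetrical. The figure is about 5% at SD 20 and 1% at SD 15. The smaller SDs fit the instrument better and are used as the main illustration.

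**4. One effect, several odds ratios.** At SD 20 the standardised difference is 18.13/20 = 0.907. Unadjusted odds ratios for the same 18.13-point effect:

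- Cut midway between the arms: 0.325 v 0.675, odds ratio 4.3.
- Cut 1 SD above the control mean: 0.159 v 0.463, odds ratio 4.6.
- Cut 1 SD below the control mean: 0.841 v 0.972, odds ratio 6.5.

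**5. Simulation of the adjusted analysis.** Assumptions: normal scores, 40 per group, true difference 18.13, pre-test correlation 0.3, and five further covariates unrelated to the score. The logistic model and the ANCOVA contain the same terms. Cuts are at the pooled 25th, 50th and 75th percentiles, with several thousand trials per setting.

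| SD | Three cuts disagree on p < 0.05 | Power, logistic at the median | Power, ANCOVA |
|---|---|---|---|
| 15 | 10–15% | 98–99% | 100% |
| 20 | about 33% | about 90% | about 98% |
| 29 (fits the scale poorly) | just over 50% | about 61% | about 78% |

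With no true effect, at least one of the three cuts is significant in about 14 to 15% of trials, against 5% for a single fixed analysis.

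**The case against.** The logistic sentence comes after the hypotheses and is offered as a further look at variables that may influence the results. It reads as supplementary, and nothing gives it decisive weight. That stands in part: the plan does not call the adjusted analysis supportive either, and Study Variables relies on comparing crude with adjusted estimates.

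Four stronger readings are tempting, and the documents do not support them:

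- **That the main comparison is compromised.** It is not. The G1 versus G2 comparison can be run on the scores without any logistic model, and its power is not lost.
- **That the power loss is the one at SD 29.** That SD is back-solved and conflicts with the bounded scale. In addition, 18.13 is described as an improvement. If it is a difference in change, the back-solved figure is an SD of change, and at correlation 0.3 with equal pre- and post-test SDs the score SD would be 28.9/√(2 × 0.7) ≈ 24.4.
- **That someone will search for a favourable cut.** Nothing says so. The plan promises complete reporting and results without manipulation. The 14 to 15% shows what the freedom would permit, not what is expected.
- **That a logistic model is wrong in itself.** With a prespecified event or ordinal form it would be usable, though a split score would still cost power.

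**Conclusion.** The concern holds for the adjusted analysis only and should be fixed before the data are seen. That the adjusted estimate is undefined follows from the text alone and needs no assumption about the SD.

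The size is illustrative. At SDs that fit the instrument, the choice among three ordinary cuts changes the significance verdict in about a third of trials (SD 20) or 10 to 15% (SD 15). Splitting at the median costs about 8 percentage points of power against ANCOVA at SD 20 (98 − 90) and 1 to 2 at SD 15. These figures rest on normal scores, 40 completers per group, a true difference of 18.13 and a pre-test correlation of 0.3. The 14 to 15% false-positive figure is a no-effect calculation, so it does not rest on the SD, but it applies only if an analyst may pick among the three cuts.

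**What to change.** Replace the logistic sentence under Approach to the Analysis Framework with:

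> For each outcome, a linear regression (ANCOVA) of the 16-week score on arm and pre-test score, adjusted for age, gender, level of education, time of diagnosis and comorbidities, will be fitted, and the adjusted mean difference with 95% CI reported.

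Add one sentence, fixed before data are seen, saying whether this or the unadjusted G1 versus G2 comparison is primary. If robust standard errors are wanted, commit to them in advance. They address unequal variance rather than skewness, so their use should not hang on how the residuals look. If a logistic model is kept, define the event and cut-off, or the ordinal form, for each outcome in advance and label the model supportive.

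**Cost.** No new data and no more patients, since the pre-test scores and the five covariates are already to be collected. With one term per covariate the model has 8 coefficients, leaving 80 − 8 = 72 residual degrees of freedom, against 78 for the t-test. Education entered as categories would use more. If no covariate is prognostic, power falls slightly: at SD 29, where the effect is easiest to see, about 76% against 79% unadjusted.
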